7.2.9 Routine Urine analysis (UA)

7.2.10 TSH, free T3, free T4

7.2.11 EKG at baseline

7.3 Evaluation During Treatment

7.3.1 Physical exam at the start of each cycle (\pm 4 days) and documentation of all concomitant medications.

7.3.2 CBC, platelet count, differential once weekly (\pm 4 days) for the first 3 cycles, then every 2-4 weeks (differential can be omitted if WBC is \leq 0.5 $\times 10^9/L$)

7.3.3 Creatinine, total bilirubin, ALT, or AST once weekly (\pm 4 days) for the first 3 cycles, then every 2-4 weeks.

7.3.4 TSH, free T3, free T4, total cortisol once monthly (\pm 4 days) for the first 3 cycles, then every 3 cycles (\pm 4 days).

7.3.5 EKG once monthly on Day 1 (+/-4 days) of each cycle

7.3.6 Bone marrow aspiration on day 28 (+/- 7 days) for Arms 1 and 2, or on Day 21 (+/-4 days) on Arm 3, then repeat bone marrow every 1-3 cycles. Bone marrow tests can be ordered more frequently if mandated by development of peripheral blood counts. No repeat bone marrow is necessary if nonresponse or progressive disease can be unequivocally diagnosed from peripheral blood tests or, in patients with a WBC $<$ 0.3 if the bone marrow test is considered noncontributory by the investigator at any time point.

7.3.7 Concomitant medication data will not be collected or entered into the case report form except for concomitant hydroxyurea and cytarabine; however, the subject's medication record will contain a list of concomitant medications.

7.3.8 Correlative Studies relating to immunologic response (Optional Consent for PA13-0291)

Tumor tissue, blood samples and bone marrow aspirate will be collected on a separate IRB approved laboratory protocol for immune monitoring as previously published [63-66], under the supervision of the Immunotherapy Platform (IMT lab Protocol PA13-0291). Patients will be consented separately on the IRB approved consent for protocol PA13-0291. Patients may participate in protocol 2014-0861 irrespective of

whether they choose to participate on protocol PA13-0291. In tumor tissues, immunohistochemical studies will be performed to evaluate tumor and immunological cell markers such as CD4 and CD8 T cells. In peripheral blood, we will also evaluate tumor and immune cell populations including but not limited to CD4 and CD8 T cells in pre and post therapy samples.

Peripheral blood up to 45 mL (within 24 hours) will be collected under an IRB-approved laboratory protocol (IMT lab protocol PA13-0291) for testing of biomarkers at the following time points

-Baseline (prior to 5-azacytidine dose), on day 14 (prior to nivolumab), and between days 21 to 28 on cycle 1 (done at MD Anderson).

In Arm 3: baseline (prior to azacitidine dosing), on Day 2 and 8 (prior to nivolumab dosing), Day 14, and Day 22 (prior to nivolumab dosing)

-In each subsequent cycle blood samples will be obtained on day 1 (prior to 5-azacytidine dose) and day 14 (prior to nivolumab dose) when possible.

In Arm 3 in each subsequent cycle blood samples will be obtained on Day 1 (prior to azacitidine dose), on Day 2 and 8 (prior to nivolumab dosing), Day 14, and Day 22 (prior to nivolumab dosing)

-Samples will be collected at progression whenever possible.

Bone Marrow:

-Bone marrow samples for PA13-0291 will be collected under an IRB-approved laboratory protocol for testing of biomarkers at baseline, at day 28 (+/- 7 days) or in Arm 3 at Day 21 (+/- 4 days), then every 1-3 cycles, and at progression. All correlative samples are optional.

All these samples can be obtained +/- 3 days. Missed samples for correlative studies will not constitute protocol deviations.

7.3.9 Study specific correlative studies relating to biomarkers and patient response mechanisms will be collected under the clinical trial, up to 40mLs of peripheral blood and up to 10mls of bone marrow aspiration. Samples will be banked for later use or sent fresh to Notable labs (blood samples only).

Bone marrow aspiration samples may be collected whenever the patient has a bone marrow procedure scheduled for study evaluations as described in sections 7.2 and 7.3.

Peripheral blood samples may be collected up to 20mls on the following schedule:

Baseline (prior to 5-azacytidine dose), on Day 7, on day 14 (prior to nivolumab), and between days 21 to 28 on cycle 1 (done at MD

Anderson).

In Arm 3: baseline (prior to azacitidine dosing), on Day 2 and 8 (prior to nivolumab dosing), Day 14, and Day 22 (prior to nivolumab dosing)
-In each subsequent cycle blood samples will be obtained on day 1 (prior to 5-azacytidine dose) and day 14 (prior to nivolumab dose) when possible.

In Arm 3 in each subsequent cycle blood samples will be obtained on Day 1 (prior to azacitidine dose), on Day 2 and 8 (prior to nivolumab dosing), Day 14, and Day 22 (prior to nivolumab dosing)

All these samples can be obtained +/- 3 days. Missed samples for correlative studies will not constitute protocol deviations.

- 7.3.10 For patients that remain on study with no significant toxicity for more than 6 months, subsequent evaluations during study may be modified after discussion with the principal investigator. These include a decrease in frequency of bone marrow aspirations to every 6-12 months (or as clinically indicated), correlative studies to every 6-12 months (or suspension of sample collection for correlative studies), other laboratory tests to once every cycle.
- 7.3.11 ALL treatments with nivolumab and/or ipilimumab must be administered at the MDACC outpatient clinic. The first cycle of azacytidine must be fully administered at the MDACC outpatient clinic. Starting cycle #2, patients will have the option of receiving 5-azacytidine injections or infusions at the MDACC outpatient clinic or local ambulatory treatment center. We do not intend for the subjects to receive the nivolumab or the ipilimumab at an outside physician's office at any time on the study. During the first cycle all the laboratory evaluations will be done at MDACC. Subsequently, the patient may have the laboratory work done at a local clinic and the results reported to the research nurse for the study. The laboratory work done at the local clinic will be forwarded to the patient's attending physician at MDACC or PI of the study, who will sign off on the labs to verify that the results have been reviewed. Patient should have end of cycle visit here at MDACC and/or prior to starting next cycle (+/- 4 days).

Outside Physician Participation During Treatment

1. MDACC Physician communication with the outside physician is required prior to the patient returning to the local physician. This will be documented in the patient record.
2. A letter to the local physician outlining the patient's participation in a clinical trial will request local physician agreement to supervise the

patient's care (Appendix H).

3. Protocol required evaluations outside MDACC will be documented by telephone, fax or e-mail. Fax and/or e-mail will be dated and signed by the MDACC physician, indicating that they have reviewed it. Changes in drug dose and/or schedule must be discussed with and approved by the MDACC physician investigator, or their representative prior to initiation, and will be documented in the patient record.

4. A copy of the informed consent, protocol abstract, treatment schema and evaluation during treatment will be provided to the local physician.

5. Documentation to be provided by the local physician will include progress notes, reports of protocol required laboratory and diagnostic studies and documentation of any hospitalizations.

6. The home physician will be requested to report to the MDACC physician investigator all life threatening events within 24 hours of documented occurrence.

7. All follow-up visits will be performed at MDACC.

8. Changes in drug dose and/or schedule must be discussed with and approved by the MDACC physician investigator, or their representative prior to initiation, and will be documented in the patient record.

| Study Period/ Cycle | Se r e | Treatment | | | | | | | | | | | | Subseq u ent Cycles | End of Study (EOS) ^h |
|--|--------------|-----------|---|--------|----|---------|----|----|----|---------|--------|--------|--------|---------------------------|---------------------------------------|
| | | Cycle 1 | | | | Cycle 2 | | | | Cycle 3 | | | | | |
| Cycle Day | | 1 | 8 | 1 5 | 22 | 1 | 8 | 15 | 22 | 1 | 8 | 1 5 | 2 2 | 1 | |
| Study Day | -14 to | 1 | 8 | 1 5 | 22 | 29 | 36 | 43 | 50 | 57 | 6 4 | 7 1 | 7 8 | | |
| Complete history | X | X | | | | X | | | | X | | | | X | |
| Physical examination ^a | X | X | | | | X | | | | X | | | | X | X |
| Performance status | X | | | | | | | | | | | | | | |
| Document all measurable disease (if present) | X | | | | | | | | | | | | | | |
| Concomitant medications ^a | X | X | | | | X | | | | X | | | | X | |

^aA

| | | | | | | | | | | | | | | | |
|---|---|---------|---|--------|---------|-------|---|---------|---|-------|---|-------------------|------------------|--------------|---|
| CBC with differential ^b | X | X | X | X | X | X | X | X | X | X | X | X | X | X | X |
| Creatinine, total bilirubin, ALT, or AST ^b | X | X | X | X | X | X | X | X | X | X | X | X | X | X | X |
| TSH, free T3, free T4, total cortisol ^c | | X | | | X | | | | X | | | | X | | |
| EKG | X | | | | X | | | | X | | | | X | | |
| Respiratory PCR panel | X | | | | | | | | | | | | | | |
| Urine analysis | X | | | | | | | | | | | | | | |
| Pregnancy test ^d | X | | | | | | | | | | | | | | |
| Bone marrow aspirate/biopsy ^e | X | | | | | X | | | | | | | X | | |
| Respiratory PCR panel and Chest XRay | X | | | | | | | | | | | | | | |
| Correlative | | Cycle 1 | | | Cycle 2 | | | Cycle 3 | | | | Subsequent cycles | | EOS | |
| Correlatives on blood ^f | | Day 1 | | Day 14 | | Day 1 | | Day 14 | | Day 1 | | Day 14 | | Day 1 and 14 | |
| Correlatives on bone marrow ^g | | Day 1 | | Day 28 | | | | | | | | | Every 1-3 cycles | | |

complete physical examination and documentation of concomitant medications will be done on day 1 of each cycle (+/- 4 days).

^bCBC with differential, creatinine, total bilirubin, ALT or AST will be done at least once weekly (+/- 4 days) for the first 3 cycles, then every 2-4 weeks on subsequent cycles.

^cTSH, free T3, free T4, total cortisol will be done at least once monthly (+/- 4 days) after the start of therapy for the first 3 cycles, then every 3 cycles (+/- 4 days) on subsequent cycles.

^dPregnancy test either urine or plasma should be done in women of childbearing potential 72 hours before initiation of protocol therapy.

^eBone marrow aspiration must be done within 28-days of initiation of therapy. Cytogenetics may be used from prior bone marrow analysis if these were not reported on the screening bone marrow.

^fCorrelative studies will be collected on peripheral blood at baseline (prior to 5-azacytidine dose), on Day 7 on day 14 (prior to nivolumab), and between days 21 to 28 on cycle 1. Subsequently, peripheral blood will be obtained on day 1 and day 14 of each cycles, and at progression if possible. All these tests can be

+/- 3 days

^gCorrelative studies will be collected on bone marrow at day 28 (+/- 7 days), then every 1-3 cycles, and at progression.

^hEOS visits include a physical examination, CBC with differential and platelets and a limited chemistry profile (total bilirubin, serum creatinine, SGPT or SGOT). A bone marrow aspiration may be done if non-response or progressive disease cannot be unequivocally diagnosed from peripheral blood.

Data regarding adverse events will be collected during the study. Please see **Appendix D** regarding data capturing of adverse events and adverse events source documentation.

Protocol specific data will be entered into PDMS/CORe. PDMS/CORe will be used as the electronic case report form for this protocol. Only unexpected AEs will be recorded in the Case Report Form (CRF). The Principal Investigator will sign and date the AE log per each patient at the completion of each course. Following signature, the AE log will be used as source documentation for the adverse events for attribution.

Treatment may be discontinued for a variety of reasons, including patient withdrawal, investigator decision, and reasons specified by the protocol. Reasons for discontinuation of treatments are described below.

8.1 CRITERIA FOR RESPONSE:

Response Criteria for AML

Response criteria will be modified from the International Working Group for AML [67]. Responders are patients who obtain a CR, CRI, or PR, with or without cytogenetic response, hematologic improvements, and morphologic leukemia-free state. Briefly, criteria are as follows:

8.1.1 Complete remission (CR):

- ◆ Peripheral blood counts:
 - No circulating blasts
 - Neutrophil count $\geq 1.0 \times 10^9/L$
 - Platelet count $\geq 100 \times 10^9/L$
- ◆ Bone marrow aspirate and biopsy:
 - $\leq 5\%$ blasts
 - No Auer rods
 - No extramedullary leukemia

8.1.2 Complete Remission with Incomplete Platelet Recovery (CRp):

For patients to be classified as being in CRp, they must achieve CR except for incomplete platelet recovery ($< 100 \times 10^9/L$).

8.1.3 Complete remission with incomplete blood count recovery (CRi):

- ◆ **Peripheral blood counts:**
No circulating blasts
Neutrophil count $<1.0 \times 10^9/L$, or
Platelet count $<100 \times 10^9/L$
- ◆ **Bone marrow aspirate and biopsy:**
 $</= 5\%$ blasts
No Auer rods
No extramedullary leukemia

8.1.4 Partial remission:

- ◆ All CR criteria if abnormal before treatment except:
- ◆ $>/=50\%$ reduction in bone marrow blast but still $>5\%$

8.1.5 Morphologic leukemia-free state:

- ◆ Bone marrow: $</=5\%$ myeloblasts

8.1.6 Hematologic Improvement (HI):

Hematologic response must be described by the number of positively affected cell lines.

- ◆ **Erythroid response (E)** (pretreatment Hgb $<11 \text{ g/dL}$)
Hgb increase by $>/=1.5 \text{ g/dL}$
- ◆ **Platelet response (P)** (pretreatment platelets $<100 \times 10^9/L$)
Absolute increase of $>/=30 \times 10^9/L$ for patients starting with $> 20 \times 10^9/L$ platelets
Increase from $< 20 \times 10^9/L$ to $> 20 \times 10^9/L$ and by at least 100%
- ◆ **Neutrophil response (N)** (pretreatment ANC $<1.0 \times 10^9/L$)
At least 100% increase and an absolute increase $> 0.5 \times 10^9/L$
- ◆ **Blast response (B)**
 $>/=50\%$ reduction in peripheral blood or bone marrow blasts but still $>5\%$

9 DISCONTINUATION OF TREATMENT:

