| Median cycles to response | 2 [1 – 13] | 2 [1 – 9] | 2 [1 – 6] |
| Median follow up, in months | 27.2 [21.7 – 35.1] | 11.8 [| 51 [0.1 – 64.8] |
| 4 weeks mortality | 3 (4) | 0 | 12 (7) |
| 8 weeks mortality | 10 (14) | 2 (8) | 34 (20) |

Abbreviations: N, number, CR, complete remission, CRi, complete remission with incomplete count recovery, PR, partial response, HI, hematologic improvement

*Hematologic improvement in one or more parameter maintained >6 months on study

[@]Stable disease (SD) was defined as the absence of CR, CRi, PR, MLFS, HI without evidence of clinical deterioration or proliferative disease, maintained >6 months on study. This particular response was not captured for control.

2.3 E

Venetoclax in AML (Background and unmet need)

--Venetoclax plus HMA in patients with newly diagnosed AML

An ongoing phase Ib/II study has reported promising safety and efficacy of venetoclax in combination with either azacitidine or decitabine in patients ≥ 65 years of age with previously untreated AML and who are ineligible for chemotherapy (DiNardo CD et al, *Blood*. 2019 Jan 3;133(1):7-17). At the most recent update (Pollyea D et al ASH 2018 Oral presentation Abstract 285: full PowerPoint attached as Appendix), 145 patients were treated with a median age of 74 years (range, 65-86 years). Cytogenetics were poor risk in 49% of patients. The 30-day and 60-day mortality rates were 3% and 8%, respectively. Tumor lysis syndrome was not observed. The CR/CRI rate for the entire cohort was 66% with a median duration of CR/CRI of 11.0 months. The median overall survival for the entire cohort was 17.5 months. These results represent the best survival data for older, unfit patients reported to date in newly diagnosed AML. Based on these exciting results in this historically difficult-to-treat patient population, in November 2018 the US FDA approved venetoclax in combination with either LDAC, azacitidine or decitabine for patients with newly diagnosed AML who are ≥ 75 years of age or have comorbidities that preclude the use of standard intensive chemotherapy.

Emerging clinical and exposure response data have suggested that the 400mg dose of venetoclax has the best risk-benefit profile, and a phase III study of venetoclax 400mg with azacitidine in the frontline setting is ongoing and has recently completed enrollment (VIALE A).

--Unmet Need in AML and Need to Continue Improving HMA with Venetoclax

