Two ongoing trials are evaluating VEN combination regimens in treatment naïve patients with AML who are ≥ 65 years of age and who are not eligible for standard induction: (a) to evaluate the efficacy and tolerability of the combination of VEN with a methyltransferase inhibitor (azacytidine or decitabine) (ClinicalTrials.gov Identifier: NCT02203773); (b) to evaluate VEN with low-dose cytarabine (ClinicalTrials.gov Identifier: NCT02287233).

Overview of Ongoing Phase 1b Study (M14-358): Venetoclax in Combination with HMA in Treatment Naïve AML

As of 09 March 2016, a total of 45 subjects ≥ 65 years of age with treatment naïve AML ineligible to receive standard induction therapy were enrolled into the escalation stage at 3 dose levels of venetoclax at 400 mg, 800 mg, and 1200 mg. Venetoclax was administered daily during the 28-day cycles in combination with decitabine (20 mg/m^2 intravenously on Days 1 – 5 once every 28 days) or azacitidine (75 mg/m^2 intravenously or subcutaneously on Days 1 – 7 once every 28 days). Preliminary safety and efficacy data are available from the ongoing dose escalation stage of this trial.

The most common adverse events for all subjects in Study M14-358 were nausea (53.3%), diarrhea (44.4%), febrile neutropenia (40.0%), neutrophil count decreased (31.1%), platelet count decreased, cough, and fatigue (28.9% each), edema peripheral and hypokalemia (26.7% each). Events grade 3 and above were reported for the majority (91.1%) of subjects; the most common event was febrile neutropenia (40.0%). Serious adverse events were reported for 27 (60.0%) subjects, including febrile neutropenia (11 subjects), malignant neoplasm progression (3 subjects) atrial fibrillation, abdominal pain, non-cardiac chest pain, pyrexia, pneumonia, sepsis, bone pain (2 subjects each). All other events occurred in 1 subject each. The combination of venetoclax with decitabine and azacitidine demonstrates a tolerable safety profile.

As of 09 March 2016, the ORR, as assessed by the investigators for the subjects enrolled into the 3 dose levels, was 62.2% (28 of 45), with CR in 12 (26.7%), CRI in 15 (33.3%), and PR in 1 (2.2%). Four subjects (8.9%) were reported to have morphologic leukemia-free state (less than 5% blasts in bone marrow aspirate sample with at least 200 nucleated cells) after completion of Cycle 1. Eight

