- Venetoclax will be administered orally daily on Days 1-21 of the first cycle; and Days 1-14 for subsequent cycles.
- In cycle 1, patients should undergo a bone marrow aspiration and biopsy on day 21 (+/- 4 days). Patients who achieve marrow remission (i.e. bone

Nivolumab and azacytidine marrow blasts <5% by morphology) or marrow aplasia/hypoplasia (</=10% cellularity or insufficient sample) should discontinue venetoclax for the remainder of the cycle and be monitored for count recovery.

- a) If the Day 21 bone marrow shows <5% blasts, the venetoclax should be held, and cycle 2 should not be initiated till ANC>0.5 and platelets are >30K without platelet transfusion support for >5 days.
- b) If the Day 21 bone marrow shows aplasia/hypoplasia (</=10% cellularity or insufficient sample), the venetoclax should be held on Day 21, and a repeat bone marrow should be performed on Day 28 (+/- 4 days) for response and MRD assessment. If the Day 28 bone marrow shows >/=5% blasts proceed with cycle 2 if this is in the best interest of the patient (those with C1D28 bone marrow >/=5% are allowed to receive 21 days of venetoclax in cycle#2). If the Day 28 bone marrow shows <5% blasts, the venetoclax should continue to be held, and cycle 2 should not be initiated till ANC>0.5 and platelets are >30K without platelet transfusion support for >5 days. If the Day 28 bone marrow shows persistent aplasia/hypoplasia (</=10% cellularity or insufficient sample) continue to hold the venetoclax and repeat a bone marrow in approximately 10-14 days.
- c) If a bone marrow remission (<5% blasts) or aplasia/hypoplasia is not confirmed on the Day 21 bone marrow, patients should continue venetoclax until day 28 and have a repeat bone marrow on Day 28 (+/- 5 days). If the Day 28 bone marrow shows >/=5% blasts proceed with cycle 2 if this is in the best interest of the patient (those with C1D28 bone marrow >/=5% are allowed to receive 21 days of venetoclax in cycle #2). If the Day 28 bone marrow shows <5% blasts or aplasia/hypoplasia follow steps outlined in "a" and "b" above.
- d) Treatment interruptions and dosing schedules other than the ones mentioned above can be considered after discussion with the PI and proper documentation of the rationale.
- e) Of note the nivolumab infusion will continue as scheduled and will not be impacted or adjusted based on venetoclax dosing schema or venetoclax related delays.

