11.2 Sample Size

Arm 1:***Part a. Lead-in phase***

The primary objective of the lead-in phase is to determine the safety of nivolumab in combination with 5-azacytidine in patients with refractory/ relapsed AML. Up to 30 patients will be accrued into the lead-in part of the study.

Part b. Expansion phase

- A. Up to 70 patients (including 6 patients treated at the MTD from the lead-in part) with relapsed/refractory AML will be recruited for the Arm 1 Salvage cohort .
- B. Up to 40 newly diagnosed older AML patients (age ≥ 65) will be recruited for the Arm 1 Frontline older cohort .

Arm 2:**Part a. Lead-in phase**

The primary objective of the lead-in phase is to determine the safety of nivolumab with ipilimumab in combination with 5-azacytidine in patients with refractory/ relapsed AML. Up to 24 patients will be accrued into the lead-in part of the study.

Part b. Expansion phase

- A. Up to 54 patients (including 6 patients treated at the MTD from the lead-in part) with relapsed/refractory AML will be recruited for the Arm 2 Salvage cohort.
- B. Up to 30 newly diagnosed older AML patients (age ≥ 65) will be recruited for the Arm 2 Frontline older cohort.

The efficacy of the combination will be measured by the overall response rate (ORR), defined as CR (complete remission) + CR_p (complete remission with incomplete platelet recovery) + CR_i (complete remission with incomplete count recovery) + PR (partial response) + marrow clearance of blasts + hematologic improvement (HI) in platelets, hemoglobin, or ANC within 3 months of treatment initiation among adult patients with refractory/ relapsed AML AND newly diagnosed older patients with AML. ORR and toxicity will be monitored simultaneously using the Bayesian approach of Thall, Simon, Estey (1995, 1996) and the extension by Thall and Sung (1998).

Arm 3:**Part a. Lead-in phase**

The primary objective of the lead-in phase is to determine the safety of nivolumab with 5-azacytidine and venetoclax in patients with refractory/ relapsed AML. A total of 18 patients (3 dose levels with a maximum of 6 patients at each dose level) will be accrued into the lead-in part of the study.

Part b. Expansion phase

- A. A total of 30 patients (excluding 6 patients treated at the MTD from the lead-in part) with relapsed/refractory AML will be recruited for the Arm 3Salvage cohort.
- B. A total of 30 newly diagnosed older AML patients (age ≥ 65) will be recruited for the Arm 3 Frontline older cohort.

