Once safety of the MTD has been established, any patients still on study at a dose lower than MTD can be dose escalated up to MTD. Patients treated in the lead-in phase at MTD

will be included in the Phase II portion of the study.

The efficacy of the combination will be measured by the overall response rate (ORR), defined as CR (complete remission) + CRp (complete remission with incomplete platelet recovery) + CRi (complete remission with incomplete count recovery) + MLFS within 6 months of treatment initiation among adult patients with refractory/ relapsed AML AND newly diagnosed older patients with AML. ORR and toxicity will be monitored simultaneously using the Bayesian approach of Thall, Simon, Estey (1995, 1996) and the extension by Thall and Sung (1998).

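### The primary ORR has no marrow-adequacy condition for MLFS or CRi (Arm 3) and no support-free or duration condition for HI (Arms 1-2), so an aplastic marrow or a transfusion effect can be scored as a response

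*Combined protocol and SAP*

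**What the plan says.** **Arm 3.** Section 11.2 builds the primary ORR from CR, CRp, "CRi (complete remission with incomplete count recovery) + MLFS within 6 months of treatment initiation". All that 8.1.5 requires for MLFS is "Bone marrow: $</=5\%$ myeloblasts". CRi in 8.1.3 needs low counts, at most 5% marrow blasts, no circulating blasts, no Auer rods and no extramedullary leukemia. Neither definition mentions cellularity or a minimum number of cells.

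The first Arm 3 marrow is on Day 21 (7.3.6). The treatment text under 5.2.1.7 lists aplasia separately from marrow remission. Item b begins "If the Day 21 bone marrow shows aplasia/hypoplasia (</=10% cellularity or insufficient sample" and goes on to ask for a repeat marrow around Day 28 for response and MRD assessment, with another 10-14 days later if aplasia persists. Neither 8.1 nor 11.2 refers to this text. In the background on the venetoclax plus hypomethylating-agent study M14-358 (2.6), MLFS is described as "less than 5% blasts in bone marrow aspirate sample with at least 200 nucleated cells".

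**Arms 1-2.** The primary ORR in 11.2 includes "marrow clearance of blasts + hematologic improvement (HI) in platelets, hemoglobin, or ANC within 3 months of treatment initiation". Under 8.1.6 the erythroid criterion is a hemoglobin rise of at least 1.5 g/dL. The platelet criterion is either "Absolute increase of $>/=30 \times 10^9/L$ for patients starting with $> 20 \times 10^9/L$ platelets" or, from below 20, a rise above 20 that at least doubles the count. The neutrophil criterion is a doubling with an absolute rise above 0.5. No duration, confirmation or support-free interval is stated. Table 8 allows red cell, platelet and white cell transfusion, myeloid and platelet growth factors, and erythropoietin, all without restriction. The sponsor's Table 1 in 2.3 D reported HI under a stricter rule: "Hematologic improvement in one or more parameter maintained >6 months on study".

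**The concern.** A marrow emptied by treatment has few blasts because it has few cells. Read literally, it satisfies 8.1.5. If the patient is also cytopenic, with no circulating blasts, Auer rods or extramedullary disease, it satisfies CRi as well. The hematologic DLT definition (after Table 5C) describes a marrow below 10% cellularity with fewer than 5% blasts and prolonged cytopenia. That marrow also meets 8.1.5, so one patient could count both as a DLT and as a responder.

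In Arms 1-2, a hemoglobin or platelet rise after transfusion meets 8.1.6. So does a neutrophil rise after growth factor or white cell transfusion.

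ORR is the primary endpoint and also drives the futility boundaries. False responses would raise the reported rate and make it less likely that a cohort with too little activity stops.

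**Working it through.** **1. Reproduce the plan's figures.** Inputs are the printed Arm 3 boundaries in 11.3 E and F, at looks of 5, 10, 15, 20 and 25 patients:
- Futility, salvage: stop at or below 1, 3, 5, 8, 10 responses.
- Futility, frontline: stop at or below 2, 5, 9, 12, 16 responses.
- Toxicity, both: stop at or above 4, 6, 8, 10, 12.

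With response and toxicity independent, exact binomial recursion gives

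P(stop early) = 1 − P(no futility stop) × P(no toxicity stop).

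P(no toxicity stop) is 0.9994, 0.9854 and 0.8902 at true toxicity 0.10, 0.20 and 0.30. At toxicity 0.20, salvage gives 0.9840 (ORR 0.25), 0.5676 (0.45) and 0.1579 (0.60). Frontline gives 0.7985 (0.60) and 0.1344 (0.80). All equal the printed tables. The rules are correct for the ORR as counted, so the weakness lies in what is counted.

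**2. Add false responses.** The documents do not say how many non-responders would be miscounted, so the added points are assumptions. Nine points is only a yardstick, close to the MLFS rates quoted in the background (4/45 = 8.9%, 4/43 = 9.3%).

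| Cohort | True ORR | Counted ORR | P(no futility stop) | P(stop), toxicity 0.10 / 0.20 / 0.30 |
|---|---|---|---|---|
| Frontline | 66% | 66% | 0.4018 | 0.598 / 0.604 / 0.642 |
| Frontline | 66% | 71% (+5) | 0.5959 | 0.404 / 0.413 / 0.470 |
| Frontline | 66% | 75% (+9) | 0.7409 | 0.260 / 0.270 / 0.340 |
| Salvage | 25% | 25% | 0.0162 | 0.984 / 0.984 / 0.986 |
| Salvage | 25% | 34% (+9) | 0.1201 | 0.880 / 0.882 / 0.893 |
| Salvage | 45% | 45% | 0.4388 | 0.561 / 0.568 / 0.609 |
| Salvage | 45% | 54% (+9) | 0.7240 | 0.276 / 0.286 / 0.355 |

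Example (frontline, 71%, toxicity 0.30): 1 − 0.5959 × 0.8902 = 0.470.

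As shares of true non-responders miscounted, these are 5/34 = 15% (frontline +5), 9/34 = 26% (frontline +9), 9/75 = 12% (salvage at 25%) and 9/55 = 16% (salvage at 45%).

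**3. HI, Arm 2 salvage.** The same recursion on Tables 15 and 16 reproduces the printed 0.6787 at ORR 0.15 and toxicity 0.20. If 5% of non-responders were miscounted, the counted ORR would be 0.15 + 0.05 × 0.85 = 0.1925. P(stop) over toxicity 0.10-0.30 would then fall from 0.68-0.72 to 0.40-0.48. The 5% is again an assumption.

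**The case against.** **The plan already defers aplastic marrows.** Item b of 5.2.1.7 calls for a repeat marrow for response assessment, and an insufficient sample yields no blast percentage. This stands against the tempting reading that an aplastic Day 21 marrow is always scored as a response. The supportable wording is that it can be, because the deferral sits in treatment text that the response criteria do not invoke.

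**The cited source may supply the conditions.** Section 8.1 gives its criteria briefly and as modified from a published working-group paper. That paper is not available here. Since the criteria are described as modified, the omitted conditions cannot be assumed to apply.

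**The background rates do not measure the bias.** A reader might take the 9-12% MLFS rates (4/45, 4/43, 4/33) as the inflation. They are not aplasia rates, and the 4/45 is described with the 200-cell rule, so those marrows would still count. Likewise, the HI responders in Table 1 (7 of 23 and 2 of 11) had HI maintained beyond 6 months, so they do not size a transient transfusion effect. Patients aplastic at Day 21 who reach CR or CRi within 6 months are responders anyway. Only those who never properly qualify inflate the ORR.

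**An inactive salvage triplet would still usually stop.** This is correct at the 25% null, where the probability stays at 88-89% even with 9 added points. The loss is larger at intermediate activity and in the frontline cohort.

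**The benchmarks are not all stricter.** Two of the salvage venetoclax series in 2.3 E count MLFS in their ORR (9/43 and 21/33), and their MLFS definitions are not given. In M14-358 the ORR of 28/45 is CR 12 + CRi 15 + PR 1 and excludes MLFS. That is a separate question of comparability.

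**Arm 1 is closed** (70 salvage, 15 frontline). For HI, the prospective effect is therefore on Arm 2; in Arm 1 only reporting is affected.

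**Conclusion.** The point holds as a gap in the primary endpoint definition. Applied literally, 8.1.3 and 8.1.5 allow an aplastic Arm 3 marrow to count as a response, and 8.1.6 allows supported or transient count changes to count in Arms 1-2. The plan's own treatment text, its description of MLFS in M14-358 and its Table 1 footnote all use stricter concepts, so this is more than missing detail.

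The documents do not show that such misclassification has occurred or how often it would. Conditional on the assumed added points, the effect on stopping is modest for salvage at the design null (98-99% to 88-89% with 9 points). It is material for salvage at 45% (56-61% to 28-36% with 9 points) and for frontline at 66% (60-64% to 40-47% with 5 points). These figures assume that response and toxicity are independent and that the added points are net of patients who later qualify.

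**What to change.** In 8.1, with 11.2 pointing to it:
- Require an adequate marrow for MLFS, CRi and marrow clearance of blasts: for example at least 200 nucleated cells, and not aplastic or insufficient as 5.2.1.7 defines these. Marrow clearance of blasts has no definition of its own and needs one. Changing 8.1.5 alone would leave the CRi route open.
- Add no circulating blasts and no extramedullary disease to MLFS.
- Cross-refer to the repeat-marrow text in 5.2.1.7, and state that an aplastic marrow is not a response until a repeat marrow qualifies. Reconcile the blast cut-offs when doing so: 5.2.1.7 uses below 5%, and 8.1 uses 5% or below.
- Count HI only if it is unsupported in that lineage (transfusion or growth factor) and sustained for a minimum that the sponsor states.
- For Arm 1-2 patients already treated, disclose any change of rule as an amendment, or report the stricter ORR as a sensitivity analysis beside the existing one.

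**Cost.** The reported ORR may be slightly lower. The marrow conditions are mostly wording. The HI rule needs more, because concomitant medications other than hydroxyurea and cytarabine are not entered in the CRF (5.6, 7.3.7). Transfusion and growth-factor use would have to be abstracted from charts or captured prospectively. No change to treatment or to the marrow schedule is implied.
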